8.2 Data Analysis

The clinical data will be entered and stored in InForm™ database. Statistical analysis will be conducted.

A safety review will be conducted by the IDSMC after Part I. A final analysis will be conducted at the end of the study. Analyses will include an intent to treat (ITT) analysis including all participants enrolled and a per protocol analysis using all participants who complete the study without major protocol violations.

Histograms and boxplots will be used to check the distribution and possible outliers for continuous variables. Continuous variables that follow a normal distribution will be summarised using means and standard deviations. Skewed continuous variables will be summarised using medians and inter-quartile ranges. Categorical variables will be summarised using frequencies and percentages.

8.3 Primary and Secondary Endpoint Analysis

All participants who receive at least one dose of Pembrolizumab will be included in the safety analysis set.

The frequency of AEs will be assessed for severity (NCI CTCAE v4), expectedness, seriousness and causal relationship to IMP. In addition, AEs will be summarised by toxicity type, impact on IMP and by timing.

All participants who receive at least one dose of Pembrolizumab and undergo disease re-evaluation as per protocol will be included in the efficacy analysis.

Due to sample size constraints, for the primary outcome of assessing the safety and tolerability of Pembrolizumab following TACE and secondary outcomes of ORR every 3 months and QOL, we will use descriptive measures such as frequencies and percentages for categorical variables and means and standard deviations for normally distributed continuous variables, as specified above in section 8.1.

The secondary endpoint of PFSR will be estimated by the Kaplan-Meier method. This rate estimates the proportion of participants who do not progress and are alive at a given time of 12 weekly timepoints. The PFSR is calculated from the start of Imp administration until the date of progression or death from any cause.

Univariate models will be performed for all demographic and other study variables, as statistically appropriate, as well as to test for confounding due to sample size constraints, with models such as Fisher's exact test or the Chi-square test utilised for categorical variables and t-tests or the Wilcoxon test (if the continuous variable does not follow a normal distribution) for continuous ones. For all estimates, 95% confidence intervals will be calculated.

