- Due to the peculiar immune-mediated toxicity related to Pembrolizumab and the kinetics of liver functional recovery following TACE a time window of 21 days is deemed biologically adequate to characterise acute liver-related toxicity emerging from Pembrolizumab treatment and will be considered as the DLT window of the study. In Part 1 and Cycle 1 only study participants will attend weekly for laboratory evaluations (Viral load if indicated, PT/INR and aPTT, haematology, biochemistry, T3, T4 & TSH, cortisol).

- In the case that DLTs are observed only in the Child Pugh B7 participants but not in the Child Pugh A participants, only Child Pugh A participants will be recruited to the expansion cohort as determined by the IDSMC.
- The overall safety profile of Pembrolizumab will be fully characterised during the whole study period, including a safety follow up (SFU) visit 30 ± 7 days post-discontinuation and a telephone follow-up visit 130 ± 7 days after the last IMP dose.
- A review will be conducted at the end of Part I by the IDSMC. A final analysis will be conducted at the end of the study. Analyses will include an intention to treat (ITT) analysis including all participants enrolled and a per protocol analysis using all participants who complete the study without major protocol violations.

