5.1.2.6 Tumour Imaging and Assessment of Disease

Tumour imaging may be performed by chest CT, dual phase CT or contrast enhanced MRI scan of the abdomen at screening and every 12 weeks thereafter. Baseline CT/MRI scans do not need to be repeated if obtained within 35 days of TACE. Tumour imaging only needs to be conducted during the EOT if participant has come off study for reason other than disease progression and has not had a scan in the previous 6 weeks.

Tumour imaging will be assessed centrally as per mRECIST criteria.

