5.4.2 Follow-up Visits

Participants who discontinue will move into the Follow-Up Phase and should be assessed by telephone follow up every 8 weeks (+/-7 days) to collect information regarding disease status, survival status, and details of new anti-cancer therapy initiated. For up to 130 days post last dose, their AE/SAE will be followed up as well.

Follow-up will continue until the last participant has completed the study, either with disease progression, unacceptable toxicities, withdrawal or completion of 1 year of treatment.

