8.0 STATISTICAL ANALYSES

8.1 Sample Size and power considerations

Since this is the first time that Pembrolizumab is given to participants with chronic viral infection and limited functional liver reserve, we designed the study as a safety-oriented trial and considered enrolling a subsequent cohort of up to 26 participants following an initial safety run-in of 6 subjects to: 1) satisfy the safety aims of the study; 2) preliminarily document the efficacy of treatment to inform subsequent efficacy-testing in a future adequately powered trial; 3) obtain adequate information regarding the disease-modulating effects from treatment reflected by the proposed translational endpoints.

With primary endpoints being safety, no power calculation for hypothesis testing is required to formally power the study: the upper 95% confidence interval for toxicity events will inform the decision to proceed to a future, adequately powered phase II trial. Using the rule of three, if zero events are observed in 26 participants the upper 95% confidence interval will be 15%.

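### If the Section 8.3 efficacy set governs PFSR, dosed participants who die by week 12 without a scan after first dose are events left out, and each omission raises the 12-week rate

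*Combined protocol and SAP*

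**What the plan says.** All of the following is in the combined protocol and SAP.

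- **Efficacy set (Section 8.3).** "All participants who receive at least one dose of Pembrolizumab and undergo disease re-evaluation as per protocol will be included in the efficacy analysis". Disease re-evaluation is not defined further. The safety set in the same section needs only one dose.
- **PFSR (Section 8.3).** The estimator is Kaplan-Meier. On the meaning of the rate: "This rate estimates the proportion of participants who do not progress and are alive at a given time of 12 weekly timepoints". On the time origin and the event: "The PFSR is calculated from the start of Imp administration until the date of progression or death from any cause".
- **Scan schedule.** Section 5.1.2.6 allows chest CT with dual-phase CT or "contrast enhanced MRI scan of the abdomen at screening and every 12 weeks thereafter". Section 5.3 counts assessment days from Cycle 1 Day 1, which puts the first scheduled on-treatment scan at about week 12. Section 5.1.2.6 and footnote 2 of Table 3 add an end-of-treatment scan for participants who come off for a reason other than progression and have had no scan in the previous 6 weeks.
- **Other analysis populations.** Section 8.2 states: "Analyses will include an intent to treat (ITT) analysis including all participants enrolled", together with a per-protocol analysis. Section 1.5 repeats this. Neither section ties either population to an endpoint.
- **Status of efficacy.** Section 1.4.2 makes efficacy secondary and exploratory. It also describes the 12-weekly PFS rate as the share without progressive disease and does not mention death.

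**The concern.** The entry condition and the event definition in Section 8.3 pull against each other. Death is an event in its own right and needs no scan to establish it. Yet entry to the efficacy set requires a re-evaluation, and someone who dies before the first scheduled scan may never have one. Such a person has failed on the endpoint but cannot join the set in which the endpoint is estimated. Section 8.3 has no rule that brings these deaths back.

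What is at stake is the meaning and later use of the estimate. Section 8.1 says the trial is meant to document efficacy in a preliminary way, to inform testing in a later, adequately powered trial. A 12-week PFSR that omits early deaths would look better than the rate its own definition describes.

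**Working it through.** The documents give no target PFSR, no expected rate and no expected number of early deaths, so there is no planned figure to reproduce. The check covers direction and size.

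**Inputs**
- Event, time origin, estimator and analysis set: Section 8.3.
- First scheduled on-treatment scan at about week 12: Sections 5.1.2.6 and 5.3.
- n = 32 dosed (assumed). Section 3.1 gives 32 as the maximum number of evaluable participants. Because of the replacement rules in Sections 3.1.1 and 3.1.2, the number dosed could be higher.
- s progression-free and alive at week 12 (assumed): 16, 20 or 24, that is 50%, 62.5% or 75%.
- k deaths by week 12 with no scan after first dose (assumed): 0, 1 or 2.

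**Size, with no censoring before week 12**

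All dosed: s/n. Section 8.3 set: s/(n − k). Difference: s·k / [n(n − k)].

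| s | All dosed | k = 1 | k = 2 |
|---|---|---|---|
| 16 | 16/32 = 50.0% | 16/31 = 51.6% (+1.6) | 16/30 = 53.3% (+3.3) |
| 20 | 20/32 = 62.5% | 20/31 = 64.5% (+2.0) | 20/30 = 66.7% (+4.2) |
| 24 | 24/32 = 75.0% | 24/31 = 77.4% (+2.4) | 24/30 = 80.0% (+5.0) |

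For s = 20 the exact 95% intervals are 43.7 to 78.9 (all dosed), 45.4 to 80.8 (k = 1) and 47.2 to 82.7 (k = 2). With k = 0 the two sets agree. For a given rate, a larger n makes the shift slightly smaller.

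**Direction when there is censoring**

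Take away one event by week 12 that had m participants at risk.
- Its own factor (m − 1)/m drops out, so the estimate is multiplied by m/(m − 1).
- At each earlier event the risk set falls from n_i to n_i − 1, which multiplies the estimate by 1 − 1/(n_i − 1)².
- Every n_i − 1 is at least m, so the product of these terms telescopes to more than (m − 1)/m.
- The net factor is therefore above 1 whenever the estimate is above 0.

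A simulation of 20,000 data sets with random censoring agreed. Leaving out a death by day 84 never lowered the estimate. It made no difference in 6 data sets, all with an estimate of 0.

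**Where the direction stops**

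- *Unscanned death after week 12.* This person was event-free at week 12. Leaving one out of the 20 gives 19/31 = 61.3% against 20/32 = 62.5%, a fall of 1.2 points.
- *Living participant without a scan.* Suppose 32 are dosed, with one progression at day 20, one unscanned participant last known alive at day 40, and eight progressions at week 12. The Section 8.3 set gives 22/31 = 70.97%. In the all-dosed set the result depends on how that participant is handled:
  - censored at day 40: 31/32 × 22/30 = 71.04%, so exclusion lowers the rate slightly;
  - censored at first dose: 70.97%, so exclusion changes nothing;
  - counted as a failure: 22/32 = 68.75%, so exclusion raises it.

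**How many deaths might there be?**

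Section 1.1.1 says survival at this stage often exceeds 2 years. Assuming exponential survival with a median of M years, expected deaths by day 84 are 32 × [1 − 2^(−84/(365.25M))]: 2.5 for M = 2, 1.7 for M = 3 and 1.3 for M = 4. These are deaths of any kind. The number without a scan is probably lower, since entry requires good performance status and liver function and some who die will have been scanned.

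**The case against.** The strongest reply is that Section 8.2 already promises an intention-to-treat analysis of everyone enrolled, which contains these deaths. A reader who infers that the plan discards early deaths altogether therefore goes too far. What remains is that this analysis is attached to no endpoint, while Section 8.3 names a different set for efficacy. It also includes people who were never dosed (Sections 3.1.1 and 3.1.2 provide for withdrawal before pembrolizumab), and they have no PFSR start date. It cannot be run for PFSR without a rule that the plan does not give.

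Second, re-evaluation is undefined. If the contrast scan about 30 days after TACE (Section 6.1) counted, deaths after dosing would stay in the set. The text does not rule this out. It is the less natural reading, because that scan comes before the first dose and is described as standard care after TACE. The point therefore stays conditional on the reading.

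Third, the end-of-treatment scan narrows the route. Some participants who deteriorate and stop before week 12 will be scanned and so enter the set. That stands, and it reduces the number of deaths affected without removing the gap.

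Fourth, a reader might infer that every unscanned exclusion inflates PFSR. The worked cases show otherwise: the direction is established only for deaths by week 12.

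Finally, PFSR drives no decision. Section 8.1 looks to toxicity: "the upper 95% confidence interval for toxicity events will inform the decision to proceed to a future, adequately powered phase II trial". This stands, and it is why the issue is minor.

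**Conclusion.** The point holds in conditional form. If the Section 8.3 set governs PFSR and re-evaluation means a scan after first dose, deaths by week 12 without such a scan are events under the definition but lie outside the set, and each omission raises the 12-week Kaplan-Meier PFSR. At an assumed 32 dosed and a PFSR of 50 to 75%, one such death adds 1.6 to 2.4 points and two add 3.3 to 5.0. The documents do not fix the number of such deaths, and it may be zero. Even two would shift the estimate little against a 95% interval about 35 points wide.

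Severity is minor. The documents do not support reading this as a threat to the primary safety analysis, which uses all dosed participants, or to the decision on a phase II trial. The harm is that the reported rate may not be the one defined, and that the plan leaves open which population it refers to.

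**What to change.** In Section 8.3:
- estimate PFSR by Kaplan-Meier in all participants who received at least one dose, with no re-evaluation condition;
- count death without a scan as an event on the date of death;
- censor living participants who have no scan after first dose at first dose;
- state that this set governs PFSR.

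In Section 8.2, say which endpoints the intention-to-treat set serves. Keep the re-evaluated set for tumour response, or as a sensitivity analysis for PFSR.

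Two steps are optional: a further sensitivity analysis that counts living unscanned participants as failures, and aligning the PFSR wording in Section 1.4.2 with Section 8.3 so that both require being alive.

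The cost is wording only. No added visits or data are needed, because Section 5.4.2 already has participants who discontinue "assessed by telephone follow up every 8 weeks (+/-7 days) to collect information regarding disease status, survival status". The one downside is that the reported PFSR may be slightly lower; with no such deaths, this change costs nothing.

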8.4 Exploratory Endpoint Analysis

The sample collection will be used for future ethically approved research. For the translational/exploratory endpoints, appropriate descriptive measures as well as univariate models will be shown as dependent on whether the relevant measure is categorical or continuous, whether the test is paired or not and whether is it normally or non-normally distributed as indicated above.

9.0 REGULATORY, ETHICAL AND LEGAL ISSUES

9.1 Declaration of Helsinki

The CI will ensure that this study is conducted in full conformity with the principles of the 1964 Declaration of Helsinki and any subsequent revisions.

9.2 Good Clinical Practice

The study will be conducted in accordance with the guidelines laid down by the International Conference on Harmonisation for Good Clinical Practice (ICH GCP E6 guidelines).

9.3 Research Ethics Committee Approval

9.3.1 Initial Approval

Prior to the shipment of IMP and the enrolment of subjects, the REC must provide written approval of the conduct of the study at named sites, the protocol and any amendments, the Participant Information Sheet (PIS) and Informed Consent Form (ICF), any other written information that will be provided to the participants.

9.3.2 Approval of Amendments

Proposed amendments to the protocol and aforementioned documents must be submitted to the HRA/REC and Medicines Healthcare Regulatory Agency (MHRA) (as required) for approval as instructed by the Sponsor.

Amendments that are intended to eliminate an apparent immediate hazard to participants may be implemented prior to receiving Sponsor or REC approval. However, in this case, approval must be obtained as soon as possible after implementation.

9.3.3 Annual Progress Reports

The REC will be sent annual progress reports in accordance with national requirements.

9.3.4 Annual Safety Reports and End of Trial Notification

The REC will be sent annual safety updates in order to facilitate their continuing review of the study (reference. ICH GCP E6 Section 3.1.4) and will also be informed about the end of the trial, within the required timelines.

9.4 Regulatory Authority Approval

The study will be performed in compliance with the regulatory requirements of the UK.

Clinical Trial Authorisation from the appropriate Regulatory Authority will be obtained prior to the start of the study. In addition, the Regulatory Authority must approve amendments (as instructed by the Sponsor), receive Suspected Unexpected Serious Adverse Reactions (SUSAR) reports, Development Safety Update Reports and be notified of the end of the trial.

9.5 Insurance and Indemnity

Imperial College holds Public Liability ("negligent harm") and Clinical Trial ("non-negligent harm") insurance policies which apply to this trial.

9.6 Trial Registration

The study will be registered on the *clinicaltrials.gov* trial database in accordance with requirements of the International Committee of Medical Journal Editors (ICMJE) regulations.

9.7 Informed Consent

The PI/delegate at each site will:

- Ensure that each participant is given full and adequate oral and written information about the study including the background, purpose and risks/benefits of participation
- Ensure that each participant is notified that they are free to withdraw from the study at any time
- Ensure that each participant is given the opportunity to ask questions and allowed sufficient time to read and understand the ICF
- Ensure each participant provides signed, dated ICF before undergoing any study specific procedure
- Ensure the original copy of the signed, dated ICF is stored in the ISF and a copy is also filed in the participant's medical records
- Ensure that each participant receives a copy of the signed, dated ICF

9.8 Contact with General Practitioner

It is the PI/delegate responsibility to inform the participant's General Practitioner by letter that the participant is taking part in the study provided the participant agrees to this, and information to this effect is included in the PIS and ICF.

9.9 Subject Confidentiality

The PI/delegate must ensure that the subject's confidentiality is maintained. On all documents submitted to the Sponsors, participants will be identified by a trial ID number only. Documents that are not submitted to the Sponsor (e.g. signed ICF) should be kept in a strictly confidential file by the PI/delegate.

The PI/delegate shall permit direct access to participant's records and source document for the purposes of monitoring, auditing, or inspection by the Sponsor, authorised representatives of the Sponsor, Regulatory Authorities and RECs.

9.10 Data Protection

Precautions will be taken to ensure that participant confidentiality is preserved at all times. The PI/delegate will identify those individuals who will require access to participant data and identifiable details and obtain appropriate permission from the consenting participant.

9.11 End of Trial

The EOT is defined as the last participant last visit (LPLV).

9.12 Study Documentation and Data Storage

The PI must retain essential documents until notified by the Sponsor, and for at least 25 years after study completion. Participant files and other source data (including copies of protocols, original reports of test results, IMP dispensing logs, correspondence, records of informed consent, and other documents pertaining to the conduct of the study) must be retained. Documents should be stored in such a way that they can be accessed/data retrieved at a later date. Consideration should be given to security and environmental risks.

No study document will be destroyed without prior written agreement between the Sponsor and the CI/delegate. Should the PI wish to assign the study records to another party or move them to another location, written agreement must be obtained from the Sponsor & CI/delegate.

10.0 DATA MANAGEMENT

10.1 Source Data

All original records and certified copies of original records of clinical findings, observations, or other activities necessary for the reconstruction and evaluation of the trial are classified as source data.

Source data are contained in source documents; these are defined as: original documents, data, and records e.g., hospital records, clinical and office charts, laboratory notes, memoranda, participant's diaries or evaluation checklists, pharmacy dispensing records, recorded data from automated instruments, copies or transcriptions certified after verification as being accurate copies, microfiches, photographic negatives, microfilm or magnetic media, x-rays, subject files, and records kept at the pharmacy, at the laboratories and at medico-technical departments involved in the clinical trial.

10.2 Language

CRFs will be in English. Generic names for concomitant medications should be recorded in the eCRF wherever possible. All written material to be used by participants must use vocabulary that is clearly understood, and be in the language appropriate for the study site.

10.3 Database & Data Management

Data will be recorded using the InForm electronic data capture (EDC) and management system where possible.

AE data will be coded using the Medical Dictionary for Regulatory Activities (MedDRA) system organ class (SOC) and preferred term (PT), and CTCAE v4.0 grade.

Data queries will be raised for inconsistent, impossible or missing data. All entries to the study database will be available in an audit trial.

10.4 Data Collection

Details of procedures for eCRF completion will be provided in a study manual.

11.0 STUDY MANAGEMENT STRUCTURE

11.1 Independent Data & Safety Monitoring Committee

This study will employ an Independent Data Safety Monitoring Committee (IDSMC)

The IDSMC is an independent body that will act in an advisory capacity to monitor the safety of participants participating in this study. The IDSMC will review the safety data and recommend modifications to the protocol to ensure participant safety, or recommend early termination of the study if major concerns arise about the participant's safety at any time during the course of the study. The IDSMC will review the safety profile of the IMP at the completion of Study Part 1 and should any SUSAR occur during the course of the study. The roles and responsibilities of the IDSMC will be outlined in a separate charter agreed to by each of the members of the IDSMC.

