3.0 STUDY DESIGN

3.1 Design

The study will be performed at 1-4 sites in the UK and will recruit up to a maximum of 32 evaluable participants. This study is an OL, single arm, sequential phase study evaluating safety, tolerability and preliminary efficacy of sequential TACE followed by Pembrolizumab and will be conducted in two parts.

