3.1.1 Part One

Part 1 of the study will consist of a safety run-in of up to 6 participants treated with Pembrolizumab at the clinically recommended dose of 200 mg Q3W. Subjects will be observed for determination of DLTs over a 21 day time window with weekly laboratory assessments in Cycle 1 only (Viral load if indicated, PT/INR and aPTT, haematology, biochemistry, T3, T4 & TSH, cortisol). Particular attention will be given to liver function tests (LFT). Whilst no DLTs were observed nor Maximum Tolerated Dose (MTD) was defined in dose escalation studies of Pembrolizumab monotherapy, the safety run-in phase of this study will allow us to verify protocol procedures and assess the safety of the combination with TACE. The decision to undertake the main feasibility trial for the TACE followed by 200 mg dose with at least 30 days interval or to increase the window between TACE and Pembrolizumab to at least 45 days will be made by the IDSMC who will consider the general safety profile with a particular focus on acutely occurring liver-related toxicity.

If there are zero DLTs and no other safety concerns the feasibility trial will be undertaken using the standard 200 mg Q3W dose with at least 30 days window between TACE and Pembrolizumab. If there are one to two DLTs, the IDSMC will then advise to continue with either at least 30 days interval or to increase the window between TACE and Pembrolizumab to at least 45 days for the expansion cohort based on additional information and general safety profile. If three or more DLTs are observed in the six participants of the safety run-in the trial will be stopped.

In the safety run-in and at the start of the feasibility trial, as a safety measure, participants 2-6 will be dosed after an interval of one week following the first dose received by the first participant.

Accounting for the great heterogeneity of participants presenting with intermediate-stage HCC, at least 1 participant in Part 1 will be mandated to correspond to Child Pugh B7 class criteria which will ensure wide generalisability of the safety outcomes to the full spectrum of severity of background liver dysfunction.

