3.1.2 Part Two

Once the data for 6 patients are reviewed by the IDSMC in part 1 a further 26 evaluable participants will be recruited to the study with the same regimen - TACE followed by 200 mg Pembrolizumab after at least 30

days window or with TACE followed by 200 mg after at least 45 days. This will further characterise the safety and tolerability of Pembrolizumab in this population.

In this part of the study, if a participant withdraws or is withdrawn from the study prior to completion of the first 21 day treatment period, in the absence of a DLT, that participant must be replaced. If a participant is withdrawn for any reason before receiving Pembrolizumab, replacement with an additional participant will be allowed.

Participants entering part two of the study must be assessed up to 28 days prior to TACE to confirm eligibility and be recruited onto the trial. They will be scheduled for Pembrolizumab dosing as per agreed time window determined by IDSMC and will be given Pembrolizumab every Q3W \pm 3 days until radiologically confirmed disease progression, unacceptable toxicity, withdrawal or a maximum of 1 year of treatment has been completed.

If the pembrolizumab dosing scheduled is set at 45 days after TACE, at least 1 participant will be mandated to meet Child-Pugh B7 criteria in the safety run-in phase to ensure wide generalisability of the safety outcomes to the full spectrum of severity of background liver dysfunction.

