7.8 Definition of Suspected Unexpected Serious Adverse Reaction (SUSAR)

Any SAR that is NOT consistent with the applicable product information as set out in the IB.

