11.3 Early Discontinuation of the Study

Early trial termination can occur for well-documented reasons.

Further recruitment of participants will not take place under the following conditions:

- Premature termination of the trial.
- Drug-related events, i.e. SUSARs, emerging adverse effects that are serious and the risk/benefit ratio is unacceptable.
- Procedure-related events, i.e., the recruitment rate is too low or the number of dropouts for administrative reasons is too high

In the event of MSD decision to no longer supply the IMP, ample notification will be provided so that appropriate adjustments to participant treatment can be made.

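### As far as the protocol shows, Part 2 (26 of 32 participants) has no numeric toxicity boundary and no scheduled IDSMC review; the only review event named after Part 1 is a SUSAR.

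*Combined protocol and SAP*

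**What the plan says.** **Size.** Section 3.1 says that the study "will recruit up to a maximum of 32 evaluable participants". Six are in Part 1, and section 3.1.2 says that "a further 26 evaluable participants will be recruited to the study" after the IDSMC has seen the run-in data.

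**Part 1.** Section 3.1.1 gives a numeric rule, repeated in section 6.5: "If three or more DLTs are observed in the six participants of the safety run-in the trial will be stopped". With one or two DLTs the IDSMC chooses between a TACE-to-pembrolizumab interval of at least 30 days and one of at least 45 days for Part 2.

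**Part 2.** The 21-day window is still used, but only for replacement. Section 3.1.2 says of a participant who leaves "prior to completion of the first 21 day treatment period, in the absence of a DLT, that participant must be replaced". No rule uses the Part 2 DLT count.

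**Review.** Section 8.2 states: "A safety review will be conducted by the IDSMC after Part I. A final analysis will be conducted at the end of the study". Section 11.1 adds one event: "The IDSMC will review the safety profile of the IMP at the completion of Study Part 1 and should any SUSAR occur". Section 7.8 defines a SUSAR as "Any SAR that is NOT consistent with the applicable product information as set out in the IB".

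**General powers.** Section 11.1 also lets the IDSMC recommend early termination whenever major safety concerns arise. Section 11.3 ends recruitment for SUSARs or for "emerging adverse effects that are serious and the risk/benefit ratio is unacceptable". Section 11.1 leaves the committee's roles and responsibilities to a separate charter.

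**The concern.** Safety is the primary objective, and 81% of the participants who inform it (26/32) are in Part 2. The toxicity of most interest is hepatic. Sections 1.2.2 and 6.8.3 already describe immune-related hepatitis as a pembrolizumab reaction, so such cases may well be judged expected under section 7.4.3. They would then not be SUSARs, and repeated cases would not by themselves call for an IDSMC review under the protocol.

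A sequence that is too toxic but passes a six-person run-in by chance could therefore be given to the whole expansion cohort without meeting any pre-stated point at which the independent committee compares the count with a limit. The gap would matter most if the interval is lengthened to 45 days, because the six run-in participants will have been treated on the 30-day schedule.

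**Working it through.** **Step 1. Reproduce the plan's total.** Table 1 (section 3.2): 6 + 26 = 32. The Part 2 share is 26/32 = 81%.

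**Step 2. Trace what reaches the IDSMC in Part 2.**
- SAEs (section 7.4.1) go to the sponsor and chief investigator, then to the drug manufacturer.
- Immune-related events of clinical interest (section 6.8.2) go to the sponsor and chief investigator, then to the manufacturer.
- Other events of clinical interest (section 7.5) go to the chief investigator, then to the manufacturer.
- SUSARs (section 11.1) prompt an IDSMC review.

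Only the last route names the committee. The confidence limit in section 8.1 informs a later phase II trial, not continuation of Part 2.

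**Step 3. Operating characteristics of the run-in rule.** The plan states none and names no unacceptable DLT rate, so the true 21-day rate p is assumed over a range. The numeric rule lets the trial continue when 2 or fewer of 6 have a DLT:

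P(pass) = (1−p)^6 + 6p(1−p)^5 + 15p²(1−p)^4

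At p = 0.40: 0.0467 + 0.1866 + 0.3110 = 0.544. At p = 0.50: (1 + 6 + 15)/64 = 0.344.

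The expected number of Part 2 participants with a DLT, if all 26 are treated, is 26p.

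| Assumed DLT rate | P(pass run-in) | Expected with a DLT in Part 2 |
|---|---|---|
| 10% | 98.4% | 2.6 |
| 20% | 90.1% | 5.2 |
| 25% | 83.1% | 6.5 |
| 33% (1/3) | 68.0% | 8.7 |
| 40% | 54.4% | 10.4 |
| 50% | 34.4% | 13.0 |

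These are the properties of the numeric rule alone. The IDSMC could act on its judgement with fewer DLTs.

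**Step 4. Would repeating the run-in ratio in Part 2 close the gap?** This is a check, not a proposal. Take a trigger at half of participants with a DLT, looked at after 6, 12, 18 and 24 in Part 2. An exact binomial recursion gives a trigger probability of 37.6% at a 33% rate. The chance of passing the run-in and then completing Part 2 untriggered is 0.680 × (1 − 0.376) = 0.424, or 42%. A boundary therefore has to be chosen from its own trigger probabilities, not copied from Part 1.

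**The case against.** The strongest reply is that Part 2 is not unsupervised, and much of it stands.

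- The IDSMC may recommend termination at any time (section 11.1), and section 11.3 halts recruitment for serious emerging effects. Neither is limited to unexpected events. A reader might infer that Part 2 has no toxicity trigger at all, or that a SUSAR is the only way the committee can act. The documents do not support that. What is missing is a count, a schedule and a data route.
- A reader might also infer that nobody has to look at Part 2 toxicity before the final analysis. That is wrong too. SAEs and events of clinical interest are reported within 24 hours, hepatic events of clinical interest require treatment to be held and a hepatology consultation (section 6.8.3), and annual safety reports go to the regulator and ethics committee (sections 7.10, 9.3.4). These are looks at individual cases, or annual reports. None is an independent review of the cumulative count against a limit.
- The charter may schedule Part 2 reviews. It is not supplied, so absence can be asserted only for the protocol. The Part 1 rule is in the protocol, however, and its Part 2 counterpart would belong beside it.
- The IB is not supplied either. That severe hepatic events after TACE would be judged expected is likely but not established.
- It is tempting to say that a 45-day schedule would certainly be tried with no run-in. Section 3.1.2 refers to a Child-Pugh B7 participant in the safety run-in phase if 45 days is adopted, and section 3.1.1 staggers first doses at the start of the feasibility trial. The first may imply a second run-in, but no size, rule or review is given for one, and Table 1 shows none.

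**Conclusion.** The point holds for the protocol as supplied. Part 2 has no numeric toxicity boundary and no scheduled IDSMC review, and nothing written sends accumulating IB-consistent toxicity to the committee. The general powers in sections 11.1 and 11.3 are real but unquantified.

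The size depends on the assumed rate. If the true DLT rate is 20% or less, the run-in is nearly always passed and the gap costs little. At 33% to 50%, the run-in rule still lets the trial proceed with probability 68% down to 34%, and about 9 to 13 of the 26 would be expected to have a DLT.

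The figures assume a common DLT rate in both parts, independent participants and full enrolment of Part 2. A change to 45 days may alter the rate. Confidence is high on what the protocol says, and lower on what happens in practice, which turns on the charter and the IB.

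**What to change.** In sections 3.1.2, 8.2 and 11.1, and in the charter:

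1. Schedule IDSMC reviews during Part 2 of cumulative 21-day DLTs and related SAEs, for example when the first 6 and the first 12 Part 2 participants complete the window. Count afresh if the interval changes to 45 days.
2. Have the sponsor and IDSMC set a Part 2 review boundary and state its trigger probabilities over a range of DLT rates. The supplied text does not list which events qualify as a DLT, so the definition should be stated or cross-referenced with the boundary.
3. Send treatment-related deaths and related serious hepatic events to the IDSMC whether or not they are expected.

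Two sets of passages must also be reconciled. The mention in section 3.1.2 of a safety run-in phase at 45 days does not match section 3.1.1 and Table 1. Table 3, note 1, requires weekly Cycle 1 blood visits in both parts, whereas sections 1.5, 3.1.1 and 5.1.2.7 give them for Part 1 only. The second affects whether the Part 2 data for these reviews would be complete.

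**Cost.** Protocol and charter wording, and one or two extra meetings of the existing committee, with no extra participants. A review could briefly pause first doses. Participants who have had TACE and are waiting for cycle 1 would be affected, so the plan should say how they are handled.
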